Adverse events, serious adverse events, death, laboratory data, vitals, ECG and ECHO, will be assigned to the study time periods defined below. Partial dates will be imputed into full dates, if applicable, for slotting data to the appropriate categories below (see Section 4.4). Flag variables (time in relation to study treatment) indicating the study time periods will be added to these datasets.

Pre-therapy is defined as the time prior to the subject's first dose of study treatment.

On-therapy is defined as the time from first dose of study treatment until 30 days after the last dose date of study treatment.

Post-therapy is defined as any time beyond the on-therapy period.

Some datasets include the first dose day as On-therapy and some exclude the first dose date as On-Therapy. The first dose day (Day 1) is considered pre-therapy for ECOG, ECG, vital signs, liver events, lab tests, and cardiac scan. The first dose day (Day 1) is considered to be On-therapy for adverse events and concomitant medications.

Study time period for concomitant medications and blood and blood supportive care products

Concomitant Medication and Blood and Blood Supportive Care Product start and end dates will be assigned to study time periods in relation to first dose of study treatment as defined below. The start date reference time flag variables and end date reference time flag variables will be added to the concomitant medications and blood and blood supportive products datasets, respectively.

Start relative to treatment: Assign to 'BEFORE' if start date is prior to study treatment start date or if subject has not taken any study treatment or (start date is missing and end date is before study treatment start date). Else assign to 'DURING' if the start date falls on or between the first and last dose dates of study treatment or if subject is ongoing (not all study treatment

discontinuation records completed) or start date is missing. Else assign to 'AFTER' if start date is after the on-therapy period.

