End relative to treatment: Assign to 'BEFORE' if end date is prior to study treatment start date or if subject has not taken any study treatment. Else assign to 'DURING' if end date falls on or between the first and last dose dates of study treatment or if subject is ongoing (not all study treatment discontinuation records completed) or (end date is missing and start relative to treatment not 'AFTER'). Else assign to 'AFTER' if start date is after the on-therapy period or (end date is missing and start relative to treatment='AFTER').

Only on-therapy blood and blood supportive care products that start after the start of study treatment are included in the Blood Products and Blood Supportive Care Product summaries. Therefore, for summary tables, include blood and blood supportive care product records where start relative to treatment in ('DURING') and end relative to treatment in ('DURING','AFTER'). All data will be reported in listings.

Concomitant medication start relative to treatment and end relative to treatment flags are used to select data to include in the Concomitant Medication summaries as follows:

- **Summary of Concomitant Medications:** This summary will contain medications including those with start date prior to study treatment start date and continue (missing end date or end date after study treatment start date) on therapy. Note that any medications with start date and end date prior to study treatment start date will be excluded. In addition, any medication that was started during post-therapy will be excluded. Include concomitant medication records where start relative to treatment in ('BEFORE','DURING') and end relative to treatment in ('DURING','AFTER').
- **Summary of Concomitant Medications with On-Therapy Onset:** This summary will contain medications with start date after study treatment start date. In addition, any medication that was started during post-therapy (see above for definition of post-therapy) will be excluded. Include concomitant medication records where start relative to treatment in ('DURING') and end relative to treatment in ('DURING','AFTER').

Other derivations or data handling procedures related to this analysis plan are given in section 4.

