2.3.4 Prior, concomitant and post therapies

Concomitant medications will be coded using WHO Drug coding dictionary, summarized, and listed. The summary of concomitant medications will show the number and percentage of subjects taking concomitant medications by Ingredient. Multi-ingredient products will be summarized by their separate ingredients rather than as a combination of ingredients. Anatomical Therapeutic Chemical (ATC) classification Level 1 (Body System) information will be included in the data listing only. In order to be considered a concomitant medication, the concomitant medication must have been taken at some point during the on-therapy window.

Prior anti-cancer therapy will be coded using WHO Drug coding dictionary, then summarized by type of therapy and listed. Separate tables will be produced displaying prior medications by ingredient (counting multiple ingredients taken as part of a combined treatment on separate rows) and displaying combination regimens as single rows e.g. cisplatin + gemcitabine. Combined regimens will be defined based on common start dates of each ingredient, which are entered separately on the eCRF. A summary of the number of prior anti-cancer therapy regimens will also be produced.

Prior anti-cancer radiotherapy and prior cancer and non-cancer surgical procedures will be listed.

The number and percentage of subjects that received chemotherapy, immunotherapy, hormonal therapy, biologic therapy, radioactive therapy, small molecule targeted therapy, radiotherapy and cancer-specific surgery as post study treatment anti-cancer therapy will be summarized.

Summary statistics for the time from study treatment discontinuation to the first post study treatment anti-cancer therapy (in weeks) will also be included in this summary table.

Follow-up anti-cancer therapy will be coded using WHO Drug coding dictionary, then summarized by ingredient. A listing of the type of follow-up anti-cancer therapy received (chemotherapy, immunotherapy, hormonal therapy, biologic therapy, radioactive therapy, small molecule targeted therapy) and details of the anti-cancer therapy for each subject will be provided.

Anti-cancer radiotherapy and both cancer- and non-cancer related surgical procedures will be listed separately.

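### The SAP's end-date flag for concomitant medications and blood products tests the start date, so records running past the last dose drop out of the summaries

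*SAP*

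**What the plan says.** SAP section 2.1.1 defines the flags in sequence.

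- Start flag. After the BEFORE test: "Else assign to 'DURING' if the start date falls on or between the first and last dose dates of study treatment", or if the subject is ongoing or the start date is missing. Then: "Else assign to 'AFTER' if start date is after the on-therapy period".
- End flag. First: "Assign to 'BEFORE' if end date is prior to study treatment start date or if subject has not taken any study treatment". Then: "Else assign to 'DURING' if end date falls on or between the first and last dose dates of study treatment", or if the subject is ongoing, or if the end date is missing and the start flag is not AFTER. Finally: "Else assign to 'AFTER' if start date is after the on-therapy period or (end date is missing and start relative to treatment='AFTER".
- On-therapy period. "On-therapy is defined as the time from first dose of study treatment until 30 days after the last dose date of study treatment".

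The Summary of Concomitant Medications keeps records with "start relative to treatment in ('BEFORE','DURING') and end relative to treatment in ('DURING','AFTER". The on-therapy-onset and blood-product summaries use the same end-flag condition but require a start flag of DURING.

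Section 2.3.4 adds that, to be considered concomitant, "the concomitant medication must have been taken at some point during the on-therapy window".

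**The concern.** The last branch of the end flag looks carried over from the start flag: it asks when the record began, not when it ended. A medication begun before or during treatment and stopped after the last dose then has no valid end flag, yet all three summaries require one of DURING or AFTER. Separately, the start flag's DURING stops at the last dose while its AFTER begins 30 days later, leaving a hole in between.

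What would be lost is supportive care around discontinuation, such as steroids, antibiotics and transfusions. Adverse events are slotted as on-therapy through day 30 after the last dose, so the safety tables would count late events while some of the treatment given for them was missing from the companion tables. Protocol section 10 requires medications to be reported up to 30 days after the last dose, so the rule would also discard data collected for that very window.

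**Working it through.** There is no sample-size or error-rate figure to reproduce. The check applies the flags and filters literally to every feasible pairing of start and end date.

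**Set-up.** A discontinued subject with illustrative days: first dose day 1, last dose day 200, on-therapy to day 200 + 30 = 230. Start and end can each fall before day 1, on treatment (days 1–200), on days 201–230, after day 230, or be missing. Pairs with the end in an earlier period than the start are impossible. That leaves 5 (start before) + 4 (start on treatment) + 3 (start days 201–230) + 2 (start after day 230) + 5 (start missing) = 19 patterns.

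**Result as written**, for records that should count as on-therapy but are excluded:

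| Start | End | Start flag | End flag | Patterns |
|---|---|---|---|---|
| Before day 1 | 201–230, or after 230 | BEFORE | none | 2 |
| On treatment | 201–230, or after 230 | DURING | none | 2 |
| 201–230 | 201–230, after 230, or missing | none | none, none, DURING | 3 |
| Missing | 201–230, or after 230 | DURING | none | 2 |

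The concomitant-medication summary wrongly omits 2 + 2 + 3 + 2 = 9 patterns. The on-therapy-onset and blood-product summaries are not meant to take records that start before treatment, so they wrongly omit 9 − 2 = 7.

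**Unreachable value.** In a discontinued subject the end flag is AFTER only when the start is after day 230, and then the start flag is AFTER too. Every filter excludes that start flag. The AFTER listed for the end flag in the filters therefore never selects a record; only the DURING part works. This indicates a slip, not a choice.

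**Against the SAP's stated intent.** The text beside the filter says the concomitant-medication summary covers records continuing past treatment start, and excludes only those that end before treatment or start post-therapy. Post-therapy is defined as beyond the on-therapy period. All nine patterns belong in the table under that text.

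**Testing repairs.**

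1. Replace start date by end date in the last branch and change nothing else. Records ending after day 230 now get AFTER. Those ending on days 201–230 still get no end flag, because DURING stops at day 200 and AFTER starts after day 230.
2. Set AFTER when the end date is later than the last dose. Every record that began by day 200, or has a missing start date, and ended later is now flagged. Records starting on days 201–230 are still lost through the start flag.
3. Repair 2, plus start-flag DURING extended to day 230. None of the nine patterns is excluded, and starts after day 230 remain excluded.

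**The case against.** The strongest reply is that this is a drafting slip with the intent written next to it. A programmer reading the descriptive text, and seeing AFTER in the filters, would probably code the end date. That is plausible, but the SAP is the specification: literal code gives wrong tables, and silently corrected code departs from the SAP without record.

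Several limits on the impact stand:

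- Records with a missing end date and a start not flagged AFTER default to DURING and are kept. A medication still running when collection stops may have no end date. However, section 4.4.5 imputes partial end dates to the earlier of month or year end and last contact, which can push a record past the last dose.
- Ongoing subjects are unaffected. Section 2.4 places the final analysis after all patients have died or transitioned off, so this branch should rarely apply. That is an inference: ongoing is defined by incomplete discontinuation records, and section 4.4.7 allows for missing exposure end dates.
- The concomitant-medication table counts subjects by ingredient, so a subject leaves a row only if every qualifying record for that ingredient is lost.
- A transfusion completed within one day cannot straddle the last dose; such transfusions are lost through the start-flag gap.
- Section 2.3.4 states a necessary condition, so the clearest contradiction lies inside section 2.1.1 itself.
- Listings show all records. New anti-cancer therapy for censoring has its own derivation (sections 4.1 and 4.4.6), so no efficacy analysis is shown to depend on these flags.

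These points narrow the consequence; none makes the rule correct.

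**Conclusion.** The concern holds. As written, for subjects with complete discontinuation records, every record that starts by the last dose and has a known or imputed end date after it is excluded from all the summaries it belongs in. So is every record starting in the 30 days after the last dose. Within those two groups the loss is total. Their share of all records, and the effect on subject-level percentages, cannot be worked out from the documents.

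The conclusion assumes that the flags are programmed as stated and that few subjects still count as ongoing at the final analysis. The damage is under-reported supportive care in descriptive tables. It is worth correcting before the tables are produced, but it does not threaten the trial's efficacy conclusions.

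**What to change.** Make two changes in SAP section 2.1.1, applied to both medications and blood products:

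- End flag: assign AFTER when the end date is later than the last dose date, or when the end date is missing and the start flag is AFTER.
- Start flag: extend DURING so that it runs from the first dose to 30 days after the last dose, matching the on-therapy definition.

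Both are needed, since either alone leaves records out. Swapping the word start for end is not enough, because it leaves ends on days 1 to 30 after the last dose unflagged. The filters can stay as they are. The cost is two wording corrections and the matching derivation code, with no new data.

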2.2 Analysis sets

As specified in the protocol, for the final analysis the Intent-to-Treat population will be used for primary analysis of efficacy endpoints. The BRAF V600E population will be used for supportive analysis of efficacy. The All Treated Subjects population will be used for Safety analysis. These analysis populations are defined below:

The Intent-to-Treat (ITT) population is defined as all enrolled subjects regardless of whether or not treatment was administered.

The BRAF V600E population is defined as all enrolled subjects regardless of whether or not treatment was administered, who obtain positive verification of the BRAF V600E mutation from a certified central reference laboratory.

The All Treated Subjects population is defined as all subjects who receive at least one dose of dabrafenib or trametinib.

A summary of the number of subjects in each of the analysis populations will be provided. A listing of subjects included in each analysis population will also be provided.

2.2.1 Subgroup of interest

Efficacy data (investigator and independent reviewer-assessed ORR, DoR, PFS and OS) will be presented for the following subgroups within the WHO Grade 3 or 4 Glioma cohort:

- By grade (3 or 4)
- By age group (18-39 or 40+)

2.3 Patient disposition, demographics and other baseline characteristics

2.3.1 Patient disposition

A summary of subject status and reason for study withdrawal will be provided for the ITT population. This display will show the number and percentage of subjects who withdrew from the study, including primary reason for study withdrawal. Reasons for study withdrawal will be presented in the order they are displayed in the eCRF. A listing of the subject disposition/end of study record for all subjects who discontinued the study prematurely will be produced.

2.3.2 Demographics and baseline data

The demographic characteristics including age, sex, race, ethnicity, child-bearing potential, baseline height and weight will be summarized and listed for each histologic cohort. The count (n), mean, standard deviation, median, minimum value, and maximum value will be computed for age, height, and weight. The count and percentage will be computed for sex, race, ethnicity, child-bearing potential, and age categories (<18, 18-64, 65-74, and 75-84, and >=85 years).

Disease history and characteristics at initial diagnosis and screening will be listed. Separate summaries of disease characteristics at initial diagnosis and screening will be provided for each histologic cohort.

Medical conditions will be graded according to the CTCAE, Version 4.0 and coded to preferred term using the MedDRA dictionary. Medical conditions present at screening will be summarized and listed.

2.3.3 Study treatment / compliance

A summary of study treatment status will be provided for the ATS population. This display will show the number and percentage of subjects who are ongoing or discontinued study and the primary reason(s) for discontinuation of study treatment. Reasons for study treatment discontinuation will be presented in the order they are displayed in the eCRF. Separate tables will be produced for dabrafenib and trametinib. Separate listings for study treatment discontinuation will also be generated for dabrafenib and trametinib.

Summary of exposure to study treatment will be provided. The summary will include subject daily dose, population level daily dose, cumulative dose, duration on treatment for dabrafenib, duration on treatment for trametinib, and duration on combination treatment. The subject average daily dose is defined as the subject's cumulative dose divided by the duration on study

treatment. For the analysis of population level daily dose, a dose on each day for each subject will be treated as an observation and the summary will be based on the dose on each individual day for all subjects. Duration on treatment for dabrafenib or trametinib is defined as months from the first dose to the last non-zero dose, regardless of dose interruption before the last non-zero dose. In addition to mean, median, min and max, duration on dabrafenib, duration on trametinib and duration on combination treatment will also be summarized in the following categories: <3 months, 3-6 months, >6-9 months, >9-12 months, >12-24 months, >24-36 months, and >36 months.

Dose reductions will be summarised by number of reductions and reasons for reductions for dabrafenib and trametinib separately.

Dose interruptions will be summarised by number of interruptions and reasons for the interruptions for dabrafenib and trametinib separately.

A summary of overall compliance based on the exposure data will be produced separately for dabrafenib and trametinib for the ATS population. Percentage overall compliance will be summarized using the mean, standard deviation, minimum, median, and maximum. In addition, percentage overall compliance will be categorized and summarized by <80%, 80%-105%, and >105%.

The calculation of overall compliance is based on the entire interval of dosing for dabrafenib and trametinib. The formula for daily dose medication is compliance (%) = [total cumulative actual dose / (duration of study treatment x prescribed dose)] x 100 where duration of study treatment is last dose-first dose +1. For dabrafenib, the prescribed dose is 300mg per day, and for trametinib, the prescribed daily dose is 2mg per day.

Listings of overall compliance will be produced separately for dabrafenib and trametinib.

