Subjects will have radiologic tests to identify target lesions and to assess disease status per protocol-defined response assessment criteria. Subjects will be evaluated following the first dose of study treatment according to the assessment schedule (see Time and Events Table, Section 7.1). Assessments may be performed more frequently if medically necessary. A treatment cycle is 28 days. Subjects will be assessed for AEs, study treatment compliance, and use of concomitant medications.

Subjects will receive dabrafenib 150 mg BID orally plus trametinib 2 mg once daily orally on a continuous dosing schedule. Subjects will undergo disease assessment of response after receiving at least 8 weeks of treatment. Dose adjustments will be made as needed based on toxicity. Subjects will continue treatment until an unacceptable toxicity, disease progression, or death occurs. Subjects who continue on treatment will undergo disease assessment according to the applicable response assessment criteria for the specific histology (i.e., for solid tumors, radiologic assessment every 8 weeks following initial response assessment). Subjects who experience disease progression will discontinue study treatments and be withdrawn from the study, unless the investigator, with approval of the Medical Lead, indicates that the subject may receive clinical benefit from continued study treatment. Once a subject discontinues treatment and/or is withdrawn from the study, a post-treatment follow-up visit will be conducted within 28 days (+7 days) after the last dose of study treatment(s) with extended follow-up visits conducted every 4 weeks (± 7 days) for the first 6 months and then every 3 months (± 14 days) thereafter.

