Dose reduction: A dose reduction below 75 mg BID for dabrafenib or below 1 mg once daily for trametinib is not allowed. If a dose reduction below 75 mg BID for dabrafenib is required, dabrafenib will be permanently discontinued, but the subjects will be allowed to continue treatment with trametinib. If a dose reduction below 1 mg once daily for trametinib is required, then trametinib will be permanently discontinued, but these subjects will be allowed to continue treatment with dabrafenib.

If both study treatments are reduced below the minimum dose levels (75 mg BID for dabrafenib and 1 mg once daily for trametinib), then both study treatments will be permanently discontinued. Subjects should complete the Follow-Up Visit and then proceed to the extended follow-up phase as indicated in the Time and Events Table (Section 7.1).

For Grade 2 or 3 laboratory abnormalities that are considered unrelated to the study treatment or those that are reversible in <48 hrs (except for liver enzymes) such as electrolyte abnormalities may continue without dose reductions.

Dose Escalation: Following a dose reduction, subjects may be re-escalated to a higher dose level with the approval of the Medical Lead. If the AE has resolved to Grade 1 or baseline at the reduced dose level, and no additional toxicities are seen after 4 weeks of study treatment at the reduced dose, the dose may be increased to the previous dose level.

Table 9 describes the dose /schedule to be used for any necessary dose modifications (based on the initial dose level of 150 mg BID) for dabrafenib.

Table 9 Dabrafenib Dose Levels

Dose Level	Dose/Schedule
0	150 mg BID
-1 (first dose reduction)	100 mg BID
-2 (second dose reduction)	75 mg BID

Table 10 describes the dose /schedule to be used for any necessary dose modifications (based on the initial dose level of 2 mg once daily) for trametinib.

Table 10 Trametinib Dose Levels

Dose Level	Dose/Schedule
0	2 mg once daily
-1 (first dose reduction)	1.5 mg once daily
-2 (second dose reduction)	1 mg once daily

Table 11 Dose Modification Guidelines – General

CTCAE Grade	Action and Dose Modification ^{1,2}
Grade 1 or Grade 2 (Tolerable)	
Any occurrence	
 Continue treatment with dabrafenib and trametinib at same dose level (no dose modification)
Grade 2 (Intolerable) or Grade 3	

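### SAP 2.3.3 measures overall compliance against the starting doses throughout, so it reports relative dose intensity and understates adherence after protocol-directed reductions or interruptions

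*SAP*

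**What the plan says.** SAP 2.3.3 gives the formula as "compliance (%) = [total cumulative actual dose / (duration of study treatment x prescribed dose)] x 100". It covers the whole period: "The calculation of overall compliance is based on the entire interval of dosing for dabrafenib and trametinib", where "duration of study treatment is last dose-first dose +1". The prescribed dose is a constant for each drug: "For dabrafenib, the prescribed dose is 300mg per day, and for trametinib, the prescribed daily dose is 2mg per day". The result is summarised as a continuous variable and also banded: "percentage overall compliance will be categorized and summarized by <80%, 80%-105%, and >105" (per cent). It is listed by subject as well.

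Protocol section 4 sets the starting regimen: "Subjects will receive dabrafenib 150 mg BID orally plus trametinib 2 mg once daily orally on a continuous dosing schedule". Protocol 8.1 then provides for lower levels. Table 9 gives dabrafenib 100 mg BID and then 75 mg BID. Table 10 gives trametinib "1.5 mg once daily" and then 1 mg once daily. The floor is explicit: "A dose reduction below 75 mg BID for dabrafenib or below 1 mg once daily for trametinib is not allowed". The same section allows dosing to be delayed for up to 21 days while toxicity resolves (longer with approval), and allows re-escalation after 4 weeks without further toxicity.

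**The concern.** A compliance percentage should compare the dose taken with the dose the subject was told to take. After a reduction under Table 9 or 10, the subject has been told to take less than 300 mg or 2 mg per day. During a directed interruption, the subject has been told to take nothing. The SAP's denominator recognises neither, so missed doses and toxicity-directed changes lower the figure in the same way.

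At stake is what the study report says about trial conduct. A subject who followed every instruction can appear in a band that is normally read as poor adherence. The error also runs the other way: a subject reduced to 100 mg BID who mistakenly kept taking 150 mg BID would score 100%.

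The ratio also adds little. SAP 2.3.3 already reports each subject's average daily dose, defined as cumulative dose over duration on treatment. The compliance figure is essentially that quantity divided by 300 or 2.

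**Working it through.** **Denominator.** 150 mg x 2 = 300 mg per day and 2 mg x 1 = 2 mg per day. The SAP's constants are exactly the level 0 doses in Protocol Tables 9 and 10.

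**Reductions.** Take a fully adherent subject with no interruption who spends a share f of the interval at a reduced level and the rest at full dose. Let r = reduced dose / full dose. Then

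compliance = 100 x [1 - f(1 - r)],

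which is below 80% only if f > 0.20/(1 - r).

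| Level | r | Share of interval above which the band is under 80% |
|---|---|---|
| Dabrafenib 100 mg BID | 200/300 = 0.667 | 0.20/0.333 = 60% |
| Dabrafenib 75 mg BID | 150/300 = 0.50 | 0.20/0.50 = 40% |
| Trametinib 1.5 mg | 1.5/2 = 0.75 | 0.20/0.25 = 80% |
| Trametinib 1 mg | 1/2 = 0.50 | 0.20/0.50 = 40% |

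**Illustrations, assuming 364 days of dosing and perfect adherence.**

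- Lasting reduction after day 84: dabrafenib 100 mg BID gives (84 + 280 x 0.667)/364 = 74.4%; trametinib 1.5 mg gives (84 + 280 x 0.75)/364 = 80.8%. The two drugs fall in different bands.
- Lasting reduction after day 182: 83.3% (dabrafenib 100 mg BID), 87.5% (trametinib 1.5 mg), and 75.0% for the lowest level of either drug.
- Lasting reduction after day 280: even the lowest level gives (280 + 84 x 0.5)/364 = 88.5%.
- Reduction for 28 days, then re-escalation: 96.2% to 98.1%, depending on drug and level.

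**Interruptions.** Because duration runs from first to last dose, days off drug stay in the denominator once dosing resumes. One 21-day directed interruption with otherwise perfect dosing gives (T - 21)/T, where T is total days. This is below 80% only if T < 105: 63/84 = 75.0% at 84 days, but 343/364 = 94.2% at 364 days.

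**Day-by-day denominator.** If the denominator were the sum of the doses prescribed on each day (0 on directed interruption days), numerator and denominator would be equal for an adherent subject. The result would be 100% at every level and for any timing. The subject who kept taking 300 mg per day after reduction to 200 mg per day would show 300/200 = 150% over those days, instead of 300/300 = 100%.

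**The case against.** The strongest reply is that the table is descriptive and its neighbours supply the missing context. SAP 2.3.3 also requires reductions and interruptions to be summarised by number and reason for each drug, with cumulative dose and average daily dose. The formula and denominator are stated openly. Protocol 6.5 handles adherence during conduct through dosing diaries, reconciliation of dispensed and taken counts, and questioning at visits. Compliance defines no analysis population in SAP 2.2 and enters no efficacy or safety analysis; no decision attaches to the 80% boundary.

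All of this stands, and it limits the consequence. It does not make the figure a measure of compliance. The separate summaries are not linked to the individual percentages, so this table alone cannot distinguish missed doses from directed changes.

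A reader might infer two stronger things. The first is that any adherent subject on a reduced dose is classed under 80%. The daily ratio is below 80% at all four reduced levels, but the band uses the whole interval and full-dose days count, so late or brief reductions stay in 80%-105%. The second is that the SAP conceals non-adherence. The separate summaries of reductions and interruptions with reasons do not support that.

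**Conclusion.** The rule is wrong for what it is called. Under the stated formula, overall compliance is relative dose intensity. It understates compliance for every fully adherent subject with a dose reduction, or with a directed interruption followed by resumed dosing. The under-80% band follows from reductions alone only above the 40% to 80% shares in the table, according to drug and level.

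The consequence is modest: one summary for each drug and the matching listings, with no effect on ORR, duration of response, PFS, OS or the safety analyses. The documents give no frequency, timing or duration of reductions, so the number of subjects misbanded is unknown. The 364-day interval and the reduction days used above are assumptions for illustration. The thresholds need only the SAP formula and the Protocol dose levels, with perfect adherence and no interruption.

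**What to change.** Relabel the existing ratio in SAP 2.3.3 as relative dose intensity. Where the eCRF records allow, add compliance as cumulative actual dose divided by the sum of the daily doses prescribed at the time, with 0 on directed interruption days, and apply the present bands to that quantity.

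Protocol 6.5 says the eCRF holds treatment start and stop dates and the dates of delays and reductions, which supports the derivation. Whether prescribed dose is held separately from dose taken cannot be confirmed, because the annotated eCRF is not among the documents. If it is not, relabel only and drop the compliance bands; that alone removes the misstatement.

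The cost is a wording change to the SAP and table shells and, for the full version, a small extra derivation. No new data collection and no change to any dosing rule is needed.
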